4 STUDY DESIGN

4.1 Overall Design

This is a single center, single-arm, open-label study to evaluate the efficacy and safety of burosumab treatment for FGF23-mediated hypophosphatemia in patients with FD/MAS. All subjects will be co-enrolled and screened through Screening and Natural History protocol 98-D-0145, a longstanding natural history study of FD/MAS protocol 98-D-0145. Up to 15 subjects will be enrolled, with the goal of a minimum 10 subjects receiving 48 weeks of burosumab treatment with week 50 for a final adverse event review. Research activity will be conducted at the NIH Clinical Center, with outpatient laboratory monitoring and burosumab self- and/or caregiver administration between NIH visits. Study subjects will be evaluated weekly on weeks 1-4 and then every two weeks for weeks 6-50.

4.2 Scientific Rationale for Study Design

An open-label study is proposed because: 1) the target population for this intervention is extremely small, making sufficient recruitment for a larger placebo-controlled study infeasible. FD/MAS is estimated to occur in approximately 1/100,000 – 1/1,000,000 individuals, and patients with clinically significant hypophosphatemia comprise only 15-30% of the overall FD/MAS population. 2) The primary endpoint of serum phosphate is an objective, quantifiable, and well-established surrogate marker that is relatively resistant to outcome assessment bias. 3) Burosumab has been well-studied in phase 2 and 3 studies in other conditions and has an overall well-established safety profile. The current study design is well-equipped to capture potential adverse effects that are specific to the FD/MAS population.

4.3 Justification for Dose

Dosing for pediatric and adult subjects will be based on current FDA-approved regimens for XLH and TIO. Doses will be adjusted to target a serum phosphate level between -1 and +2 standard deviations for age and sex. The justification for targeting a mid-high normal phosphate level is based on the following rationale: FD bone is inherently structurally unsound and poorly mineralized, and patients with FD have an overall high prevalence of skeletal morbidity compared to other FGF23 excess disorders. Even mild degrees of hypophosphatemia have been associated with increased fractures and deformities in patients with FD [1-4]. It is therefore feasible that patients with FD may experience clinical benefit from maintaining a higher therapeutic target for serum phosphate levels. The current study provides an important opportunity to investigate the safety and efficacy of this approach in patients with FD and is supported by the well-established and favorable safety profile of burosumab in phase 2 and 3 studies.

5 STUDY POPULATION

5.1 Inclusion Criteria

In order to be eligible to participate in this study, an individual must meet all of the following criteria:

1. Confirmed diagnosis of fibrous dysplasia
2. Serum phosphate <10th percentile for age and sex, AND intact serum FGF23 ≥ 30 pg/mL[16]
3. Age ≥ 1 year
4. Provision of signed and dated informed consent/assent form

5. Stated willingness of subject or Legally Authorized Representative (LAR) to comply with all study procedures and availability for the duration of the study
6. For females of reproductive potential: agreement to use highly effective contraception for during study participation. Highly effective contraception methods include:
 - Total abstinence (when this is in line with the preferred and usual lifestyle of the participant). Periodic abstinence (e.g., calendar, ovulation, symptothermal, post-ovulation methods) and withdrawal are not acceptable methods of contraception
 - Female sterilization (have had surgical bilateral oophorectomy with or without hysterectomy) or tubal ligation at least six weeks before taking study treatment.
 - Male sterilization (at least 6 months prior to screening). For female participants on the study the vasectomized male partner should be the sole partner for that participant.
 - Combination of the following (a+b or a+c, or b+c):
 - a. Use of oral, injected or implanted hormonal methods of contraception or other forms of hormonal contraception that have comparable efficacy (failure rate <1%), for example hormone vaginal ring or transdermal hormone contraception
 - b. Placement of an intrauterine device (IUD) or intrauterine system (IUS)
 - c. Barrier methods of contraception: Condom or Occlusive cap (diaphragm or cervical/vault caps) with spermicidal foam/gel/film/cream/vaginal suppository
7. For males of reproductive potential: use of condoms or other methods described above to ensure effective contraception with partner
8. Minimum body weight of 7.5 kilograms

5.2 Exclusion Criteria

An individual who meets any of the following criteria will be excluded from participation in this study:

1. Pregnancy or lactation
2. Known allergic reactions to burosomab or drug component
3. Treatment with another investigational drug within 30 days of screening
4. Treatment with burosomab within 30 days of screening
5. Have any condition which in the opinion of the PI could present a concern for subject safety or difficulty with data interpretation
6. Severe renal impairment or end stage renal disease, defined as: pediatric patients with estimated glomerular filtration rate (eGFR) 15 mL/min/1.73m² to 29 mL/min/1.73m² or end stage renal disease (eGFR < 15 mL/min/1.73m²), adult patients with creatinine clearance (CLcr) 15 mL/min to 29 mL/min or end stage renal disease (CLcr < 15 mL/min)

5.3 Inclusion of Vulnerable Participants

5.3.1 Children

Children \geq 1 year will be included in this study. Burosomab has been well-studied in children with good safety and tolerability in phase 2 and 3 studies. Children with FD have higher incidence of hypophosphatemia compared to adults [17], and are at increased risk for growth-related and skeletal complications.

5.3.2 Adults who Lack Capacity to Consent to Research Participation

Adults who lack capacity to consent may be included in this study. Due to the likelihood of direct benefit from burosumab, and the favorable safety profile of burosumab in phase 2 and 3 studies, exclusion of this population is not appropriate. Adults who lack capacity to consent will be excluded from pre- and post-treatment bone biopsies, which entail more than minimal risk without the possibility of direct benefit.

For adult subjects, the study team will do a clinical assessment to determine if they have capacity. In situations where the clinical assessment determines that the capacity is in question, an assessment by ACAT (Ability to Consent Assessment Team) will be initiated. In the situation where the subject is known not to have capacity, this study will allow a Legally Authorized Representative (LAR) to sign consent providing the legal paperwork is filed with the Admissions Department per policy (i.e., legal guardianship, durable power of attorney, next of kin, etc). Oversight for the provisions of protection for adults unable to consent will be informed by the PI. The PI will be responsible for proper implementation of the HRPP Policy 403 - Research with Subjects Lacking Capacity to Consent.

5.4 Inclusion of Pregnant Women, fetuses or neonates

Not applicable

5.5 Lifestyle Considerations

Subject will need to commit weekly and bi-weekly research procedures as well as contraception requirements.

5.6 Screen Failures

Screen failures are defined as subjects who consent to participate in the clinical trial but are not subsequently assigned to the study intervention or entered in the study. A minimal set of screen failure information is required to ensure transparent reporting of screen failure participants, to meet the Consolidated Standards of Reporting Trials (CONSORT) publishing requirements and to respond to queries from regulatory authorities. Minimal information includes demography, screen failure details, eligibility criteria, and any Serious Adverse Event (SAE).

Individuals who do not meet the criteria for participation in this trial (screen failure) because of an insufficiently low serum phosphate or low FGF23 level may be rescreened up to 3 times. Rescreened individuals should be assigned the same subject number as for the initial screening.

5.7 Strategies for Recruitment and Retention

Subjects will be recruited from the existing cohort of subjects enrolled in the protocol, Screening and Natural History of Patients with Polyostotic Fibrous Dysplasia and the McCune-Albright Syndrome (98-D-0145), and new referrals. All potentially eligible subjects enrolled onto protocol 98-D-0145 will be invited to participate in the burosumab study. The study will also be posted on ClinicalTrials.gov. Additional recruitment may proceed through referrals from worldwide clinical and research experts involved in this specialized area of mineral metabolism. Outreach through patient advocacy organizations worldwide will also be pursued. Written flyers may be distributed at patient advocacy events. Subjects may be self-referred and/or referred by the Patient Recruitment and Public Liaison Office however, prior to enrollment onto the burosumab study all subjects will need to be enrolled and screened through protocol 98-D-0145.

5.7.1 Costs

Subjects will not be billed for any research or related clinical care that participants will receive at the NIH Clinical Center for this study. The NIH Clinical Center will provide short-term medical care for any injury resulting from participation in this clinical trial.

5.7.2 Compensation

There will be no financial compensation given for participation in this study. Air/train/bus travel will be arranged by the NIH travel agency unless there are extenuating circumstances requiring the participant to book his/her own travel. For minor subjects and adults who lack capacity for consent, travel and Children's Inn/hotel accommodation will also be provided for 1 parent or LAR. Miscellaneous out-of-pocket travel expenses (e.g., baggage receipts, airport parking, taxis) will be reimbursed if a receipt is provided. Subjects traveling by car from > 50 miles will be reimbursed mileage per NIH policies. Subject copays or co-insurance for local laboratories will be paid or reimbursed if an invoice or receipt is provided.

6 STUDY INTERVENTION

6.1 Study Interventions Administration

This is an open-label study of burosomab. All subjects will receive burosomab for 48 weeks according to regimens described in the Section **6.1.2, Dosing and Administration**.

6.1.1 Study Intervention Description

Burosomab is supplied in sterile, preservative-free, clear to slightly opalescent and colorless to pale brown-yellow solution in single-dose vials containing 30 mg/mL concentrations.

Burosomab should be securely stored at 2 to 8°C and protected from light. It should not be frozen. Burosomab will be administered subcutaneously without dilution in the abdomen, upper arm, or thigh. The site of injection will be rotated. No more than 1.5 mL will be administered in a single injection. If a subject needs more than 1.5 mL per administration, multiple injections must be administered, and a different site must be used for each injection.

6.1.2 Dosing and Administration

Burosomab initiation for pediatric and adult subjects will be based on currently approved regimens for XLH and TIO.

For pediatric subjects (age < 18 years) who weigh less than 10 kg, the starting dose is 1 mg/kg of body weight, rounded to the nearest 1 mg, administered every 2 weeks. For pediatric subjects who weigh 10 kg and greater, the starting dose regimen is 0.8 mg/kg of body weight, rounded to the nearest 10 mg, administered every 2 weeks. The minimum starting dose is 10 mg up to a maximum dose of 90 mg. For adults (age 18 years and older) the starting dose regimen is 0.5 mg/kg body weight, rounded to the nearest 10 mg up to a maximum dose of 90 mg, administered every 4 weeks.

After burosomab administration, doses will be titrated in an effort to achieve a target fasting peak serum phosphate level between -1 and +2 standard deviations for age and sex (**Table 5**). If the subject's peak serum phosphate level at week 2 remains below the target range, the subject's dose may be increased at week 4 by 0.2 to 0.5 mg/kg at the discretion of the Investigator. Doses will then continue to be titrated in increments of 0.2 to 0.5 mg/kg at 4-week intervals in individual subjects to achieve the target peak serum phosphate range. If the target range is not reached for patients >18 year and older, dosing may be administered at every 2-week dosing

intervals at the discretion of the PI and adjusted in increments of 0.2 to 0.5 mg/kg to a maximum dose of 90 mg every 2 weeks.

Table 5. Burosumab Target Phosphate Ranges for Pediatric and Adult Subjects

Age (years)	Normal Phosphate Range (mg/dL)	Target Peak Serum Phosphate Range (Z-score -1 to +2; mg/dL)
1 to <5	4.3 - 6.8	4.9 - 6.8
5 to <13	4.1 - 5.9	4.6 - 5.9
13 to <16 (girls)	3.2 - 5.5	3.8 - 5.5
13 to <16 (boys)	3.5 - 6.2	4.2 - 6.2
16-18	2.9 - 5	3.4 - 5
>18	2.5 - 4.5	3 - 4.5

From: summary of age and sex-partitioned reference intervals from the CALIPER study, including thousands of healthy children and adolescents from a multiethnic population and measured using the Abbot Architect analyzer [18].

Following this initial dose titration phase, doses may be titrated at later weeks at the discretion of the PI, if there are concerns about safety, suboptimal efficacy, or if a subject has not yet achieved the target range of serum phosphate. To optimize serum phosphate levels throughout the dose cycle, Investigators may increase the dose of burosumab in 0.5 mg/kg increments in those subjects whose trough serum phosphate level (just prior to the next dose) is below the lower limit of the target range on 2 consecutive measurements performed at 4-week intervals (**Table 6**).

Table 6. Burosumab Dose Titration Scheme

Study Week	Serum Phosphate Level Z-score ¹	Dose Adjustment
Week 2	Less than -1	Increase the dose by 0.2 to 0.5 mg/kg at next dose
Week 2 6, 10 (adults)	> +2 ³	Decrease the dose by 0.2 to 0.5 mg/kg
Week 1, 2, 3 (pediatrics)		
Weeks 4, 8, 12, 16, 20, 24, 28, 32, 36, 40, 44	Less than -1 ²	Increase the dose by 0.2 to 0.5 mg/kg
	-1 to +2	Continue the current dose
	> +2 ³	Skip dose

¹ See **Table 5** for target phosphate levels according to age and sex-adjusted Z-scores

² If phosphate levels are below –1 standard deviation on 2 consecutive measurements, the burosumab dose may be increased by 0.5 mg/kg

³ If phosphate is Z-score > +2, withhold the next dose and reassess the serum phosphate level in 2 weeks. Once serum phosphate is in target range or less than Z-score –1, treatment may be restarted at 0.2 mg/kg less than prior administered dose. If more than 2 sequential phosphate measurements are > +2 Z-score range, the patient may be considered for study discontinuation.

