There are no available data on burosumab use in pregnant women to inform a drug-associated risk of adverse developmental outcomes. *In utero*, burosumab-twza exposure in cynomolgus monkeys did not result in teratogenic effects. Adverse effects such as late fetal loss and preterm birth were observed in pregnant cynomolgus monkeys, however, these effects are unlikely to indicate clinical risk because they occurred at a drug exposure that was 15-fold higher, by AUC, than the human exposure at the maximum recommended human dose of 2 mg/kg every 2 weeks and were accompanied by maternal hyperphosphatemia and placental mineralization. Currently, Women of child-Bearing Potential (WOCBP) will be consented to receive pregnancy testing prior to burosumab initiation and at intervals throughout the trial and required to utilize contraception and agree to avoid pregnancy during the experimental treatment. There is no information regarding the presence of burosumab in human milk, or the effects on milk production or the breastfed infant. Women who are breastfeeding will therefore be excluded from participating in this study.

Ectopic Mineralization

In rabbits and cynomolgus monkeys, ectopic mineralization in multiple tissues and organs was observed at doses of burosumab-twza that resulted in supra-physiologic serum phosphate levels. In a study in wild type and hypophosphatemic Hyp mice, a murine model of XLH, ectopic mineralization was markedly less in Hyp mice. In clinical trials of XLH and TIO no clinically meaningful changes related to potential ectopic mineralization were observed. Although ectopic mineralization is a known risk related to XLH disease, and is exacerbated by the current standard of care consisting of oral phosphate and/or active vitamin D supplementation, burosumab does not appear to be associated with progression of cardiac or renal ectopic mineralization beyond the natural course of pre-existing disease.

Hyperphosphatemia

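### Titration in mg/kg steps has only a flat 90 mg maximum, so a poorly responding subject under 45 kg on 2-weekly dosing can be assigned more than 2 mg/kg

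*Combined protocol and SAP*

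**What the plan says.** Section 6.1.2 starts children under 10 kg as follows: "the starting dose is 1 mg/kg of body weight, rounded to the nearest 1 mg, administered every 2 weeks". Children of 10 kg or more start at 0.8 mg/kg every 2 weeks, rounded to the nearest 10 mg. The pediatric maximum stands in the starting-dose text: "The minimum starting dose is 10 mg up to a maximum dose of 90 mg". Adults start at 0.5 mg/kg every 4 weeks, also up to 90 mg.

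On titration, the section says: "Doses will then continue to be titrated in increments of 0.2 to 0.5 mg/kg at 4-week intervals in individual subjects". Table 6 calls for an increase of 0.2 to 0.5 mg/kg when phosphate is below Z -1 at eleven points: "Weeks 4, 8, 12, 16, 20, 24, 28, 32, 36, 40, 44". The text around the table is more permissive. The first increase is left to the investigator, and after the initial phase "doses may be titrated at later weeks at the discretion of the PI". Adults who miss the target may move to 2-weekly dosing, adjusted "to a maximum dose of 90 mg every 2 weeks".

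The only maximum in mg/kg is in section 2.3.1, under Pregnancy and Lactation, where animal exposure is compared with human exposure at the "maximum recommended human dose of 2 mg/kg every 2 weeks". Section 5.1 admits subjects from 7.5 kg.

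**The concern.** The steps scale with body weight and the maximum does not. In a small child, 90 mg is a large dose per kilogram, so the maximum takes effect late or not at all during the 44 weeks of titration.

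The plan has brakes. The dose is kept when phosphate is in range and withheld above Z +2. Dose-limiting toxicities are reviewed, a low eGFR stops treatment, and there is an independent medical monitor and a DSMC. Those that respond to phosphate do nothing while it stays low, and the others act on toxicity or on review. None limits the mg/kg dose of a poor responder.

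What is at stake is exposure above the only mg/kg maximum the protocol names, in young children who are often injected at home by caregivers. Section 8.4.10 defines overdose relative to the dose assigned under the protocol, so a high dose that was properly assigned would not be reported as one. The mg/kg ranges quoted in section 2.3.1 go no higher than 2.0, so its risk assessment does not visibly cover more. Section 2.1 calls the effect on FD lesion growth unknown, and biopsies are limited to adults.

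**Working it through.** **Inputs.** From section 6.1.2: pediatric start of 1 mg/kg to the nearest 1 mg under 10 kg, or 0.8 mg/kg to the nearest 10 mg from 10 kg (minimum 10 mg); adult start of 0.5 mg/kg; steps of 0.2 to 0.5 mg/kg; maximum 90 mg. From Table 6: Weeks 4, 8, ..., 44. From section 2.3.1: 2 mg/kg every 2 weeks. From section 5.1: 7.5 kg.

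**Break-even weight.** 90 mg / 2 mg/kg = 45 kg. At 40 kg, 90 mg is 2.25 mg/kg; at 30 kg, 3.0; at 20 kg, 4.5.

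**Path.** Dose after each step = min(90 mg, previous dose + step x weight).

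Assumptions:
- Phosphate is below Z -1 at each point and the dose is raised each time.
- The 90 mg maximum applies to titrated pediatric doses.
- Weight is constant, and titrated doses are not rounded because no rounding is stated for them.
- The Week 2 row of Table 6 is not counted as an extra step.
- The 10 mg minimum applies from 10 kg upward.

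**First dose above 2 mg/kg, 0.5 mg/kg steps**
- 7.5 kg: start 8 mg (1.07 mg/kg); 1.07 + 2 x 0.5 = 2.07 at Week 8.
- 19 kg: 15.2 mg rounds to 20 mg (1.05); 1.05 + 2 x 0.5 = 2.05 at Week 8.
- 30 kg: 24 mg rounds to 20 mg (0.67); 0.67 + 3 x 0.5 = 2.17 at Week 12.
- 20 kg: 16 mg rounds to 20 mg (1.0); 2.0 at Week 8, then 2.5 at Week 12.

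**First dose above 2 mg/kg, 0.2 mg/kg steps**
- 7.5 kg: 1.07 + 5 x 0.2 = 2.07 at Week 20.
- 20 kg: 1.0 + 6 x 0.2 = 2.2 at Week 24.
- 30 kg: 0.67 + 7 x 0.2 = 2.07 at Week 28.
- 18 kg: 14.4 mg rounds to 10 mg (0.56); 0.56 + 8 x 0.2 = 2.16 at Week 32.

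The Week 8 crossings depend on starting-dose rounding. With unrounded starts of 0.8 or 1 mg/kg, the crossing is at Week 12 with 0.5 steps (2.3 or 2.5 mg/kg) and at Week 28 or 24 with 0.2 steps (2.2 mg/kg). If the 10 mg minimum also covered children under 10 kg, a 7.5 kg child would start at 10/7.5 = 1.33 mg/kg and cross sooner with 0.2 steps: 1.33 + 4 x 0.2 = 2.13 at Week 16.

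**Where the 90 mg maximum stops escalation, 0.5 mg/kg steps**
- 30 kg: 20, 35, 50, 65, 80, then 90 mg at Week 20 = 3.0 mg/kg.
- 20 kg: 20 mg plus 10 mg per step; 20 + 7 x 10 = 90 mg at Week 28 = 4.5 mg/kg.
- 40 kg: 30, 50, 70, 90 mg at Week 12 = 2.25 mg/kg.

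**Adult of 40 kg.** The start is 20 mg; three 0.5 steps of 20 mg give 80 mg (2.0 mg/kg), and the next is held at 90 mg (2.25 mg/kg). Given every 2 weeks, this exceeds the benchmark. Given every 4 weeks, it averages 2.25/2 = 1.125 mg/kg per 2 weeks and does not.

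**The case against.** The strongest reply is that 2 mg/kg is not a dosing limit of this trial. It appears once, to scale animal exposure, and no section adopts it as a limit. A phase 2 study may exceed a recommended maximum if it means to. That stands. A reader might infer that the titration rule breaks a limit the protocol set for itself, but the documents do not support this. They support only that the rule can pass the one mg/kg maximum the protocol names, without saying whether that is intended.

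A second reply is that section 4.3 bases dosing on the approved regimens, so approved limits could be taken as the frame. This helps only in part. Section 6.1.2 narrows the statement to "initiation for pediatric and adult subjects will be based on currently approved regimens for XLH and TIO", and neither section turns it into a mg/kg limit for titration.

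Third, increases are largely discretionary. A reader might infer automatic escalation to very high doses. Under the same arithmetic a 15 kg child ends at 90 mg, or 6.0 mg/kg, but only after eleven consecutive 0.5 mg/kg increases without ever reaching Z -1. That is an extreme case and not one to expect. Passing 2 mg/kg is different, since it can take as few as two or three full steps.

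Fourth, no harm is shown. Section 2.3.1 ties ectopic mineralization and nephrocalcinosis risk to raised phosphate, and the subject in question has low phosphate. This stands too.

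**Conclusion.** The gap is real, and narrow. Section 6.1.2 and Table 6 set no mg/kg ceiling. Below 45 kg, a child whose phosphate stays under Z -1 can therefore be assigned more than 2 mg/kg every 2 weeks from Week 8 to 12 (0.5 mg/kg steps) or Week 20 to 32 (0.2 mg/kg steps). The same holds for an adult under 45 kg after a move to 2-weekly dosing, without those week ranges.

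The pediatric tops of 3.0 mg/kg at 30 kg and 4.5 mg/kg at 20 kg assume that the 90 mg maximum governs pediatric titration. That is the lenient reading, because the maximum is written with the starting dose and the titration text repeats it only for adults on 2-weekly dosing. At 45 kg or more, the same assumption keeps the dose at or below 2 mg/kg.

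A reader might infer that the plan exposes children to a known toxic dose. The documents do not show this. They report no dose-related harm independent of raised phosphate, and they do not state the highest dose ever used: two of the quoted ranges are snapshots at Week 64 and Week 40, and the TIO data give only a mean. The number of subjects who would stay below Z -1 is not given and may be zero, since section 9.2 expects about 90% in range at Week 48. The point is a missing dose limit that is cheap to add.

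**What to change.** In section 6.1.2 and a Table 6 footnote:
- Cap any 2-weekly dose at the lesser of 2 mg/kg and 90 mg. This gives 15 mg at 7.5 kg, 40 mg at 20 kg, 60 mg at 30 kg, 80 mg at 40 kg and 90 mg from 45 kg.
- Leave 4-weekly adult dosing at the 90 mg maximum.
- State that rounding may not exceed the cap. At 14 kg the cap is 28 mg: the nearest 10 mg would be 30 mg (2.14 mg/kg, over the cap), rounding down to 10 mg units would give 20 mg (1.43), and 1 mg rounding gives 28 mg (2.0).
- State that a subject at the cap and still below target stays at that dose.

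If higher doses are intended, state that ceiling and support it in section 2.3.1.

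**Cost.** One sentence and one footnote in an amendment. Under the working assumptions, the pediatric cap changes no dose before Week 8. A few poor responders may stop escalating below target. Each one who would otherwise have reached it lowers the in-range proportion by up to 1/10 = 0.10 with 10 completers, or 1/15 = 0.07 with 15. In Table 7, a fall from 0.9 to 0.8 moves the interval from 0.55-1 to 0.44-0.97; Clopper-Pearson for 9/10 and 8/10 reproduces these as 0.555-0.997 and 0.444-0.975. Rounding to 1 mg also brings non-10-mg volumes to home injection in children of 10 kg or more (28 mg at 30 mg/mL is 28/30 = 0.93 mL).

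### For an early phosphate result above Z +2, Table 6 says reduce the dose while its footnote 3 says withhold it; the two need reconciling

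*Combined protocol and SAP*

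**What the plan says.** Section 6.1.2 sets doses by titration against serum phosphate, and Table 6 is the working scheme. Two of its rows deal with a Z-score above +2, and the Z-score entry in both carries footnote mark 3.

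- Early row (weeks 2, 6, 10 for adults; weeks 1, 2, 3 for pediatric subjects): "Decrease the dose by 0.2 to 0.5 mg/kg".
- Later row (every fourth week from 4 to 44): the dose is skipped.
- Footnote 3, with no restriction by week: "withhold the next dose and reassess the serum phosphate level in 2 weeks". Once phosphate is no longer above +2, "treatment may be restarted at 0.2 mg/kg less than prior administered dose".

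For a Week 2 result below -1, the table says "Increase the dose by 0.2 to 0.5 mg/kg at next dose", while the text of 6.1.2 says the "dose may be increased at week 4 by 0.2 to 0.5 mg/kg".

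Section 6.1.2.2, on dose modifications, refers the reader back to 6.1.2. The prose of 6.1.2 gives no rule of its own for a result above +2. The risk discussion in Section 2.3.1 allows for interruption, reduction or both.

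**The concern.** An investigator holding one early result above +2 finds one instruction in the row and another in the footnote attached to that row. A subject cannot receive a reduced next dose and also have that dose withheld. Two investigators, or one investigator on two occasions, could act differently and each cite the protocol.

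Three things are at stake.

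- **Safety.** Section 2.3.1 links phosphate above the upper limit of normal to a possible increase in nephrocalcinosis risk, and this row is one of the protocol's responses to it.
- **Deviations.** Section 10.9.1 defines a deviation as a departure from the approved protocol. Either action departs from one of the two instructions.
- **Adverse events.** Section 8.3.3 gives a laboratory abnormality that requires dose interruption as an example of one to record as an adverse event. Under footnote 3 an early high result fits that example; under the row it need not. Adverse events are a secondary endpoint.

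**Working it through.** The plan states no figure on this point, so the check sets the passages side by side and then applies both to the protocol's own starting doses.

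**1. Do the two Z > +2 rows conflict with each other?** The early weeks are {2, 6, 10} for adults and {1, 2, 3} for children. The later weeks are {4, 8, ..., 44}. Neither early set shares a week with the later set, so the rows do not collide. The later row, which skips the dose, also agrees with footnote 3. The conflict lies between the early row and footnote 3.

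**2. Do the early row and footnote 3 give the same next dose?** Inputs are the starting doses d in Section 6.1.2, before rounding. Under the row, the next dose is d - 0.5 to d - 0.2. Under footnote 3, the next dose is 0, with restart at d - 0.2.

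| Subject on starting dose | d (mg/kg) | Row: next dose | Footnote 3: next dose | Footnote 3: restart |
|---|---|---|---|---|
| Adult, every 4 weeks | 0.5 | 0.0 to 0.3 | 0 | 0.3 |
| Child 10 kg or more, every 2 weeks | 0.8 | 0.3 to 0.6 | 0 | 0.6 |
| Child under 10 kg, every 2 weeks | 1.0 | 0.5 to 0.8 | 0 | 0.8 |

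The next doses coincide only for an adult on 0.5 mg/kg who is given the full 0.5 mg/kg decrease. The size of the reduction differs too: a range of 0.2 to 0.5 mg/kg in the row, the single value 0.2 mg/kg in the footnote.

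**3. Does anything else settle it?** No. Section 6.1.2.2 points back to 6.1.2, the prose there is silent on results above +2, and Section 2.3.1 leaves both actions open.

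**4. Timing of the first increase.** For an adult dosed every 4 weeks, the next dose after Week 2 is Week 4, so table and text agree. A child is dosed every 2 weeks, and footnote 6 of the Schedule of Activities has outpatient labs reviewed before administration. If the Week 2 sample precedes the Week 2 dose, the next dose is Week 2 and not Week 4. If it follows that dose, the two agree. The copy available shows the schedule only from Week 26, so the order cannot be confirmed.

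**5. Distance from the primary endpoint.** The last disputed week is 10 for adults and 3 for children: 48 - 10 = 38 and 48 - 3 = 45 weeks before Week 48. Table 6 keeps adjusting doses through Week 44 under a row that agrees with footnote 3.

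**6. How many subjects?** The documents give no rate of early Z > +2 in fibrous dysplasia. The rates in Section 2.3.1 are 6% (adults with X-linked hypophosphatemia), 7% (adults with tumor-induced osteomalacia) and no events in the pediatric studies. Assuming 6% in 10 adults, the chance of at least one case is 1 - 0.94^10 = 0.46. Assuming 7% in 15 adults, it is 1 - 0.93^15 = 0.66. Extending the pediatric experience gives about zero. These rates come from other diseases and whole exposure periods, so they show only that the branch may or may not be reached.

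**The case against.** The best defence is that footnote 3 explains how the row is carried out: hold, recheck, resume lower. For adults this comes close. A Week 2 result, with reassessment two weeks later, lands on Week 4, when the next dose is due; if restart were allowed that day, the outcome would match the row at its smallest decrease. But a dose given at Week 4 has not been withheld, and any decrease above 0.2 mg/kg remains outside the footnote. For a child with a Week 1 result, the next dose falls at Week 2 and the reassessment at Week 3, so the readings separate plainly. The table also uses separate terms for decreasing and skipping, and this reading would erase that distinction.

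Other parts of the defence stand.

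- **The whole titration is not unworkable.** A reader might infer that it is. The documents do not support this: the later Z > +2 row agrees with footnote 3, and the branches for results below -1 and within range are not touched by it.
- **The upward step sizes do not contradict each other.** A reader might set the table's 0.2 to 0.5 mg/kg against the text that "Investigators may increase the dose of burosumab in 0.5 mg/kg increments". That sentence is permissive, applies after two consecutive low troughs, matches footnote 2 in substance, and names a value inside the table's range.
- **Other safeguards exist.** They include dose-limiting toxicity thresholds (6.1.2.1), laboratory review before dosing, renal ultrasound (8.3.5) and committee oversight (10.5).
- **An adult need not miss a full 4-week cycle under footnote 3.** It asks for reassessment in 2 weeks and allows restart after that.

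**Conclusion.** The contradiction is real and narrow. It concerns one result (Z above +2) at three early time points in each age group, where the row and its footnote prescribe different next doses and different reductions. The finding rests on footnote mark 3 belonging to the early row, as it appears in the text. Even if that mark were misplaced, the footnote's wording carries no week limit.

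The Week 2 timing mismatch is a lesser point: adults are unaffected while dosed every 4 weeks, and for children it depends on whether the sample comes before the dose.

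A reader might infer that the Week 48 proportion is biased, since with 10 subjects one reclassified subject moves it by 1/10 = 0.10. That arithmetic holds for any trial of 10 and does not link this conflict to a changed classification. The disputed weeks end at least 38 weeks earlier, and titration continues. The sample size and the exact confidence interval do not depend on Table 6. What is shown is the scope for inconsistent early dosing and for unclear deviation and adverse-event classification. The number of subjects affected cannot be computed from the documents.

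**What to change.** The sponsor's clinical team should reconcile the early-week Z > +2 row of Table 6 with footnote 3, for example by stating which weeks the footnote governs, so that the action and the size of the reduction agree. The Week 2 timing of the first increase should be made the same in Table 6 and in the text of 6.1.2. No view is offered here on which rule should stand, and the investigator's discretion within the stated ranges need not be removed.

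For any subject who has already had an early result above +2, the report should say which action was taken. The drug disposition record (6.2.1) and the observed administrations (6.4) should already hold much of that information.

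The cost is a wording amendment to Table 6 and Section 6.1.2, with IRB approval and the collaborators' agreement under Section 10.11.1. It needs no extra visits, tests or subjects and no change to the analysis.
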